9.2. Distributional assumptions and outlying responses

Distributional assumptions (e.g. normality of regression residuals for continuous outcomes) will be assessed visually prior to analysis; although in the first instance the proposed primary method of estimation in this analysis plan will be followed. If responses are considered to be particularly skewed and/or distributional assumptions violated, the impact of this will be examined through sensitivity analysis; this will consist of transformation of responses prior to analysis (e.g. log transformation) in the first instance. If extreme values are apparent and considered to be affecting the integrity of the analysis, a sensitivity analysis consisting of removing the outlying response(s) and repeating the analysis will be performed. Output from these analyses, if performed, will be described and presented alongside the original analysis (or included, e.g. in appendices) with the excluded values clearly labelled.

9.3. Handling missing data

In the first instance, analysis will be completed on received data only with every effort made to follow-up participants to minimise any potential for bias. To examine the possible impact of missing data on the results, and to make sure we are complying with the intention-to-treat principle, sensitivity analysis will be performed on the primary outcome measure.¹⁰ See section 9.10 for further details regarding planned sensitivity analyses.

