4.7. Sample size

Although no definitive data exists on the composite primary outcome measure, observational studies suggest potentially dramatic reductions in mortality from civilian pre-hospital PRBC¹ and military pre-hospital PRBC with thawed plasma². Following extensive consultation with experts in pre-hospital trauma resuscitation, it is considered that an absolute reduction of 10% in the proportion of participants experiencing one of the component primary outcomes is clinically meaningful for the participants and is an appropriate effect size upon which to base the power calculation.

To detect an absolute difference of 10% between groups in the proportion of participants experiencing either episode mortality or lactate clearance $<20\%/h$ in the two hours post-randomisation (i.e. from 20% in the standard care group to 10% in the group receiving PHBP) using the method of difference between proportions (2-sided Fisher's Exact Test) with 80% power, and a type 1 error rate of 5% (i.e. $\alpha=0.05$), requires 219 participants per group to be randomised, 438 participants in total. Assuming and adjusting for a 10% loss to follow-up rate, 490 participants will need to be recruited.

The interim analysis for the Data Monitoring Committee (DMC) meeting in May 2018 reported the results on the 192 participants recruited by 20th April 2018. A pooled event rate of 65% experiencing either episode mortality or lactate clearance $<20\%/h$ in the two hours post-randomisation was observed in these participants. This observed rate does not correspond with the pooled event rate of 15% assumed in the original sample size calculations. On the DMC's recommendations, this issue was discussed with the TSC in October 2018. The TSC recommended that the power calculations were framed in terms of a relative risk rather than an absolute risk, with the original target sample size of 490 unchanged.

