Assuming the pooled event rate remains at 65% and allowing for a 10% loss to follow-up rate, 490 participants will provide 80% power to detect a relative risk ratio of 0.82 (i.e. from 71.7% in the standard care group to 58.3% in the group receiving PHBP) using the method of difference between proportions (2-sided Fisher's Exact Test), and a type 1 error rate of 5% (i.e. $\alpha=0.05$). This estimated relative risk ratio is consistent with the relative risk ratios of 1.54³ and 0.70⁴ reported in two recent pre-hospital randomised controlled trials using plasma in one of the treatment arms.

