5.5. Handling protocol deviations

A protocol deviation is defined as a failure to adhere to the protocol such as errors in applying the inclusion/exclusion criteria, the incorrect intervention being given, incorrect data being collected or measured, follow-up visits outside the visit window or missed follow-up visits. We will apply a strict definition of the ITT principle and will include all participants as per the ITT population described in section 5.3 in the analysis in some form, regardless of deviation from the protocol.⁶ This does not include those participants who have specifically withdrawn consent for the use of their data in the first instance; however these outcomes will be explored as per other missing responses.

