9.4. Data manipulations

The Trial Statistician will derive all responses from the raw data recorded in the database.

Age

Lactate clearance, expressed as a percentage per hour (%/h), is calculated using the formula:

A normal lactate is taken to be ≤ 2.2 mmol/L. Achieving $\geq 20\%$ per hour lactate clearance is defined as follows in participants whose:

- a) is > 2.2 mmol/L and whose demonstrates lactate clearance of $\geq 20\%$ per hour; or
- b) is > 2.2 mmol/L, but whose is ≤ 2.2 mmol/L, regardless of the magnitude of the change; or
- c) and are both ≤ 2.2 mmol/L, regardless of the magnitude and direction of any difference

All the above will be counted as participants achieving $\geq 20\%$ per hour lactate clearance

The above can be summarised in the following table:

(mmol/L)	(mmol/L)	Required lactate clearance
> 2.2	> 2.2	$\geq 20\%$ per hour
> 2.2	≤ 2.2	Not applicable
≤ 2.2	≤ 2.2	Not applicable

Achieving $< 20\%$ per hour lactate clearance is defined as follows in participants:

- a) Whose is > 2.2 mmol/L and whose demonstrates lactate clearance of $< 20\%$ per hour; or
- b) Who die prior to interval sampling (e.g. before the measurement is taken at) For this we require the date and time of death from the exit form to determine if the participant died within two hours and 30 minutes of randomisation

The table below summarises what is considered an event (failure to achieve lactate clearance):

(mmol/L)	(mmol/L)	Lactate clearance $< 20\%$ per hour	Lactate clearance $\geq 20\%$ per hour
> 2.2	> 2.2	Failure to clear (event)	Achieves clearance
> 2.2	≤ 2.2	Achieves clearance	Achieves clearance
≤ 2.2	≤ 2.2	Achieves clearance	Achieves clearance
Dies prior to interval sampling and within 2.5 hours of randomisation		Failure to clear (event)	

There are instances where the lactate value is too high for a value to be reported, i.e. the value is out of range (OOR) of the detection level of the test. In these cases, the lactate measurement is recorded on the database as "too high to be recorded". In these instances, at database lock prior to analysis, a review of these lactate values will be undertaken independently by two statisticians blind to treatment allocation to assess whether the participant cleared their lactate or not. For example, if randomisation lactate is OOR, but the 2-hour randomisation lactate is

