s2 2, then as per the table above the participant would be considered to have achieved clearance; or if both the randomisation and 2 hour lactates are OOR, then the participant will be considered to have failed to clear. If unable to determine, then the lactate component of the primary outcome will be considered missing.

Episode Mortality

Episode mortality is defined as those participants who die during the study between time of injury/recruitment and discharge from the primary receiving facility to non-acute care (this includes participants who die on-scene). The date of discharge from acute care and date of death are recorded on the exit form. Any deaths occurring after the date of discharge from acute care are not considered to be cases of episode mortality.

Primary Outcome

The primary outcome is a composite measure consisting of episode mortality (mortality between time of injury/recruitment and discharge from the primary receiving facility to non-acute care) and lactate clearance (failure to achieve lactate clearance $\geq 20\%$ per hour in the first two hours from randomisation). Therefore, if the participant experiences either:

- a) episode mortality or
- b) a failure to achieve lactate clearance $\geq 20\%$ per hour in the first 2 hours after randomisation

they will be considered to have experienced the primary outcome. If they have survived to the point of exiting the trial through discharge from acute care and have experienced lactate clearance $\geq 20\%$ per hour in the first 2 hours after randomisation they will be considered to not have experienced the primary outcome.

All-cause mortality within 3 hours of randomisation

The time to death is calculated by (Date and Time of death - Date and Time of randomisation). If this is less than or equal to 3 hours then the participant will be coded as having experienced all-cause mortality within 3 hours of randomisation (i.e. ≤ 3 hours). If this is more than 3 hours (i.e. >3 hours), or if the participant has completed the exit form through discharge from acute care then the participant will be coded as not having experienced all-cause mortality within 3 hours of randomisation. If the Date and Time of death is not recorded, but the participant is known to have died on-scene, then it will be assumed that the participant experienced all-cause mortality within 3 hours of randomisation.

All-cause mortality within 30 days of randomisation

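### The received-data primary analysis keeps every death but drops survivors without a lactate result, which overstates the composite risk in each arm and usually pulls the relative risk modestly toward 1

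*SAP*

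**What the plan says.** Section 9.3 sets the primary missing-data rule: "In the first instance, analysis will be completed on received data only". Imputation is reserved for a sensitivity analysis.

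The derivations in section 9.4 decide who has received data:

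- **Event.** Either component is enough. A participant with episode mortality or failed clearance qualifies, and "they will be considered to have experienced the primary outcome".
- **Non-event.** Both components are needed: "If they have survived to the point of exiting the trial through discharge from acute care and have experienced lactate clearance" at the required rate.
- **Early death.** The lactate table counts as a failure a participant who "Dies prior to interval sampling and within 2.5 hours of randomisation".
- **Out-of-range lactate.** Two statisticians blind to allocation review it. "If unable to determine, then the lactate component of the primary outcome will be considered missing".

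The results shell in Appendix D6 has a row for a missing composite. The primary model in section 9.5 adjusts for intervention delivery site only. Section 9.10 plans multiple imputation with each component imputed separately, as a sensitivity analysis. Treatment arm and mortality are not among the variables it lists for the imputation model.

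**The concern.** No single sentence says that survivors without lactate are excluded, but sections 9.3, 9.4 and Appendix D6 together lead there. A death is classifiable without lactate; a survivor is not. Only survivors can lose their composite value through a missing lactate, so missingness of the composite is tied to the outcome even when missingness of lactate is pure chance. The usual defence of a complete-case analysis, that chance missingness costs precision but not validity, does not apply to this composite. Adjustment for delivery site does not repair it.

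At stake are the reported event percentages, the absolute risk difference and, in most configurations with a real benefit, the relative risk. Deaths receive more weight in the estimate than in the trial population, and an effect acting through lactate is diluted.

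**Working it through.** **Inputs from the SAP (section 4.7).** "A pooled event rate of 65% experiencing either episode mortality" or failed clearance was seen at the interim. The revised design is "from 71.7% in the standard care group to 58.3% in the group receiving PHBP", with 490 participants, 10% loss, a two-sided Fisher's exact test and a 5% type 1 error rate.

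**Reproducing the design.** 490 × 0.9 / 2 ≈ 220 analysed per arm. Exact Fisher power for 71.7% vs 58.3% at 220 per arm is 81.8%, consistent with the stated 80%. The ratio is 0.583/0.717 = 0.813 (the SAP prints 0.82); 0.813 is the reference below.

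**Assumed, because the SAP does not give them.** Episode mortality *m*, and *q*, the probability that a survivor's lactate is missing, completely at random.

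**Formula.** Let *R* be the true composite risk and *f* = (*R* − *m*)/(1 − *m*) the failure risk in survivors. Then

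received-data risk = [*m* + (1 − *m*)(1 − *q*)*f*] / [*m* + (1 − *m*)(1 − *q*)].

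Equivalently, the non-event proportion 1 − *R* is multiplied by *k* = (1 − *q*)/(1 − *q*(1 − *m*)). This is below 1 whenever *m* and *q* are above 0, so the event risk is overstated as long as some survivors clear their lactate.

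**Worked case, *m* = 40% in both arms, *q* = 20%.** *k* = 0.80/0.88 = 0.909.

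- Control: 1 − 0.283 × 0.909 = 74.3% (true 71.7%)
- PHBP: 1 − 0.417 × 0.909 = 62.1% (true 58.3%)
- Relative risk 0.836 instead of 0.813; difference 12.2 instead of 13.4 points

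**Range at the design rates (true relative risk 0.813).**

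| Mortality, control / PHBP | q = 10% | q = 20% | q = 30% |
|---|---|---|---|
| 10% / 8.1% | 0.815 | 0.817 | 0.819 |
| 20% / 20% | 0.819 | 0.825 | 0.833 |
| 40% / 40% | 0.824 | 0.836 | 0.849 |
| 45% / 36.6% | 0.820 | 0.829 | 0.838 |
| 45% / 45% | 0.825 | 0.838 | 0.853 |
| 30% / 16.6% | 0.813 | 0.814 | 0.815 |

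The last row, where the whole absolute effect is on mortality, shows near-cancellation in the ratio. The risk difference there widens slightly (13.7 points at *q* = 20%).

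**Null case.** With 65% composite risk, 40% mortality and *q* = 10% in both arms, both risks read 66.5% and the relative risk is exactly 1.

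**Power.** In the worked case 245 × 0.88 ≈ 216 per arm remain. Exact Fisher power is 80.8% at the true rates and 74.8% at the distorted ones, so the distortion itself costs about 6 points.

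**Does handling the components separately remove it?** A simulation of 200,000 per arm, with *q* = 20% and mortality 45% / 36.6%, compared received-data risk with *m* + (1 − *m*)*f*, taking *f* from survivors who have a lactate. Control: true 71.7%, received-data 74.6%, component-wise 71.7%. PHBP: true 58.4%, received-data 61.9%, component-wise 58.4%.

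**The case against.** The strongest reply is that the plan already contains the remedy: component-wise imputation, separate reporting of each component, qualifying events, and a count of missing composites by arm. On this view only the label of primary analysis is in dispute. That is partly right, and it makes the change cheap. But the headline estimate and p-value still come from the affected analysis, and the planned imputation does not list treatment arm, so it is not yet a sound replacement.

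The size is also modest. Moving from 0.813 to 0.836 is about 0.028 on the log scale, against a standard error of about 0.071 at 220 per arm: roughly 0.4 of a standard error. This stands.

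The direction rests on chance missingness. The true risk is a weighted mean of the received-data risk and the failure risk among survivors with missing lactate. The overstatement therefore reverses only if those survivors fail more often than the received-data risk. In the worked case that means above 74.3% in control and 62.1% in PHBP, against 52.8% and 30.5% in survivors with a lactate. Since undeterminable out-of-range values are one named source of missing lactate, this cannot be dismissed.

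Three stronger readings are tempting but not supported:

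- **A contradiction with intention to treat.** Section 5.5 says the analysis "will include all participants as per the ITT population described in section 5.3 in the analysis in some form", and section 9.3 assigns that role to the sensitivity analysis. The two are compatible.
- **A spurious treatment effect from unequal missingness between arms.** Unequal *q* would produce one, but nothing in the SAP indicates a gap. Appendix B places the first lactate before the box is opened.
- **A relative risk that is always biased.** The null case and the near-cancelling mix show otherwise.

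**Conclusion.** The concern holds in this form. As written, the primary analysis overstates the composite risk in each arm whenever some participants die, some survivors clear their lactate and some survivors lack a result, even if lactate is missing completely at random. With a beneficial PHBP effect the relative risk is generally attenuated and the risk difference distorted. Assuming about 40–45% mortality, the design value of 0.813 becomes about 0.82 with 10% of survivors' lactates missing and about 0.83–0.84 with 20%; at low mortality the shift is negligible. If the SAP's 10% loss were entirely survivors' lactates at 40% mortality, *q* would be 0.10/0.60 ≈ 17%.

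These sizes rest on assumed mortality and missingness and on treating the SAP's design rates as true risks. The existence of the bias in the risks follows from the SAP's own rules under chance missingness. It is worth correcting, but it does not invalidate the trial.

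**What to change.** Make the primary estimate one that treats the two components separately. Either of these would do:

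1. Use the component-wise multiple imputation already planned in section 9.10, with treatment arm and mortality added to the imputation model and the composite derived after imputation.
2. Give deaths weight 1, and weight survivors who have a lactate by the inverse of the proportion observed, by arm and delivery site.

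Keep the received-data analysis as a sensitivity analysis. Add another in which survivors with missing lactate fail more often than those observed, because out-of-range values may not be missing at random. Report the number of survivors with missing lactate by arm; the missing rows in Appendices D6 and D6a nearly give this already.

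The cost is revised wording in sections 9.3, 9.5 and 9.10 and a corrected imputation model, with no new data. The downside is that the primary result would rely on lactate being missing at random given the model, which is why the added sensitivity analysis is needed.

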9.4. Data manipulations

The Trial Statistician will derive all responses from the raw data recorded in the database.

Age

Lactate clearance, expressed as a percentage per hour (%/h), is calculated using the formula:

A normal lactate is taken to be ≤ 2.2 mmol/L. Achieving $\geq 20\%$ per hour lactate clearance is defined as follows in participants whose:

- a) is > 2.2 mmol/L and whose demonstrates lactate clearance of $\geq 20\%$ per hour; or
- b) is > 2.2 mmol/L, but whose is ≤ 2.2 mmol/L, regardless of the magnitude of the change; or
- c) and are both ≤ 2.2 mmol/L, regardless of the magnitude and direction of any difference

All the above will be counted as participants achieving $\geq 20\%$ per hour lactate clearance

The above can be summarised in the following table:

(mmol/L)	(mmol/L)	Required lactate clearance
> 2.2	> 2.2	$\geq 20\%$ per hour
> 2.2	≤ 2.2	Not applicable
≤ 2.2	≤ 2.2	Not applicable

Achieving $< 20\%$ per hour lactate clearance is defined as follows in participants:

- a) Whose is > 2.2 mmol/L and whose demonstrates lactate clearance of $< 20\%$ per hour; or
- b) Who die prior to interval sampling (e.g. before the measurement is taken at) For this we require the date and time of death from the exit form to determine if the participant died within two hours and 30 minutes of randomisation

The table below summarises what is considered an event (failure to achieve lactate clearance):

(mmol/L)	(mmol/L)	Lactate clearance $< 20\%$ per hour	Lactate clearance $\geq 20\%$ per hour
> 2.2	> 2.2	Failure to clear (event)	Achieves clearance
> 2.2	≤ 2.2	Achieves clearance	Achieves clearance
≤ 2.2	≤ 2.2	Achieves clearance	Achieves clearance
Dies prior to interval sampling and within 2.5 hours of randomisation		Failure to clear (event)	

There are instances where the lactate value is too high for a value to be reported, i.e. the value is out of range (OOR) of the detection level of the test. In these cases, the lactate measurement is recorded on the database as "too high to be recorded". In these instances, at database lock prior to analysis, a review of these lactate values will be undertaken independently by two statisticians blind to treatment allocation to assess whether the participant cleared their lactate or not. For example, if randomisation lactate is OOR, but the 2-hour randomisation lactate is

s2 2, then as per the table above the participant would be considered to have achieved clearance; or if both the randomisation and 2 hour lactates are OOR, then the participant will be considered to have failed to clear. If unable to determine, then the lactate component of the primary outcome will be considered missing.

Episode Mortality

Episode mortality is defined as those participants who die during the study between time of injury/recruitment and discharge from the primary receiving facility to non-acute care (this includes participants who die on-scene). The date of discharge from acute care and date of death are recorded on the exit form. Any deaths occurring after the date of discharge from acute care are not considered to be cases of episode mortality.

Primary Outcome

The primary outcome is a composite measure consisting of episode mortality (mortality between time of injury/recruitment and discharge from the primary receiving facility to non-acute care) and lactate clearance (failure to achieve lactate clearance $\geq 20\%$ per hour in the first two hours from randomisation). Therefore, if the participant experiences either:

- a) episode mortality or
- b) a failure to achieve lactate clearance $\geq 20\%$ per hour in the first 2 hours after randomisation

they will be considered to have experienced the primary outcome. If they have survived to the point of exiting the trial through discharge from acute care and have experienced lactate clearance $\geq 20\%$ per hour in the first 2 hours after randomisation they will be considered to not have experienced the primary outcome.

All-cause mortality within 3 hours of randomisation

The time to death is calculated by (Date and Time of death - Date and Time of randomisation). If this is less than or equal to 3 hours then the participant will be coded as having experienced all-cause mortality within 3 hours of randomisation (i.e. ≤ 3 hours). If this is more than 3 hours (i.e. >3 hours), or if the participant has completed the exit form through discharge from acute care then the participant will be coded as not having experienced all-cause mortality within 3 hours of randomisation. If the Date and Time of death is not recorded, but the participant is known to have died on-scene, then it will be assumed that the participant experienced all-cause mortality within 3 hours of randomisation.

All-cause mortality within 30 days of randomisation

The time to death is calculated by (Date of death - Date of randomisation). If this is less than or equal to 30 days then the participant will be coded as having experienced all-cause mortality within 30 days of randomisation (i.e. ≤ 30 days). If this is more than 30 days (i.e. >30 days), or if the participant has completed the exit form through discharge from acute care (i.e. was alive at discharge from acute care) then the participant will be coded as not having experienced all-cause mortality within 30 days of randomisation. If the Date and Time of death is not recorded,

but the participant is known to have died on-scene, then it will be assumed that the participant experienced all-cause mortality within 30 days of randomisation

Trauma-induced coagulopathy

A participant is considered to have experienced trauma-induced coagulopathy if the INR > 1.5. If no INR value has been recorded, the value of prothrombin time (PT) will be converted to an INR value and used instead. To convert PT to an INR, the ratio of the observed patient PT to a control PT (standardized for the potency of the thromboplastin reagent) will be calculated:

This calculation requires the control PT to be known

Organ failure-free days (OFFS)

The presence of organ failure is defined as any SOFA component score of ≥ 3 . Organ failure will be assumed to be absent if the participant is discharged from acute care and will be assumed to be present if the participant has died.

The SOFA component scores are determined from the raw values using the conversions in Tables (a)-(f) below. For each daily assessment organ failure is present if:

ANY (Respiratory, Neurological, Cardiovascular, Liver, Coagulation, Renal) ≥ 3

PaO ₂ /FiO ₂ (kPa)	Score
≥ 53.3	0
<53.3	1
<40.0	2
<26.7 and mechanically ventilated	3
<13.3 and mechanically ventilated	4

Glasgow Coma Scale (GCS)	Score
15	0
13-14	1
10-12	2
6-9	3
<6	4

Mean Arterial Pressure or inotrope requirement	Score
MAP ≥ 70 mmHg	0
MAP <70 mmHg	1
dop ≤ 5 or dop (any dose)	2
dop >5 OR epi ≤ 0.1 OR nor ≤ 0.1	3
dop >15 OR epi >0.1 OR nor >0.1	4

Bilirubin ($\mu\text{mol/L}$)	Score
<20	0
20-32	1
33-101	2
102-204	3
>204	4

Key: dop: Dopamine, dob: dobutamine, epi: adrenaline, nor: noradrenaline
Doses in []g/kg/min

Coagulation (e)	
Plateletsx10 ³ /μl	Score
≥150	0
<150	1
<100	2
<50	3
<20	4

Renal (f)	
Creatinine (μmol/L) or urine o/p	Score
≤109	0
110-170	1
171-299	2
300-440 (or <500 mL/day)	3
> 440 (or <200 mL/day)	4

Then OFFS is the number of days alive and free of organ failure in the first 30 days. Days in which a participant is on a ward will be defined as being organ failure free. For the respiratory component, days in which a participant is either on a ward or in level 2 critical care will be defined as being ventilator free.

Age of Blood Products

For each participant allocated to the PHBP, the age of each unit of administered blood products is calculated by (Date bled - Date of randomisation). If any unit is 8 days or older, that participant will be classified as receiving blood products ≥8 days old for the purposes of the subgroup analysis (see Section 9.9).

Cardiac Arrest

Participants will be classified as experiencing cardiac arrest if they have a heart rate of 0 and a blood pressure reading (systolic or diastolic) of 0 when their vital signs are recorded on-scene.

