4.11. Timing of final analysis

The final analysis for the trial will occur once all the participants have completed the trial. The main trial data collection for participants ends at withdrawal, discharge to non-acute care, death or at 30 days follow-up, whichever occurs first. Apart from episode mortality data which is collected up to discharge from acute care which may be >30 days. Final analysis will then occur only after the corresponding outcome data has been entered onto the trial database and validated as being ready for analysis. This is provided that the trial has not been stopped early for any reason (e.g. DMC advice or funding body request).

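### Secondary outcomes: the 3-hour mortality rule leaves withdrawn survivors uncoded, its second table row is conditioned on having a time of death, and untimed on-scene deaths are handled differently in the lactate component

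*SAP*

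**What the plan says.** **3-hour mortality (section 9.4).** The rule starts from the time between randomisation and death. The event branch reads: "If this is less than or equal to 3 hours then the participant will be coded as having experienced all-cause mortality within 3 hours". The non-event branch needs either a death later than that limit or an exit by discharge, in these words: "or if the participant has completed the exit form through discharge from acute care then the participant will be coded as not having experienced" the outcome. Where the time of death is missing, on-scene deaths have their own line: "but the participant is known to have died on-scene, then it will be assumed that the participant experienced all-cause mortality within 3 hours of randomisation". There is no other branch.

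**Exit from the trial (section 4.11).** "The main trial data collection for participants ends at withdrawal, discharge to non-acute care, death or at 30 days follow-up, whichever occurs first". The next sentence makes an exception: "Apart from episode mortality data which is collected up to discharge from acute care which may be >30 days".

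**Missing data.** Section 9.3: "In the first instance, analysis will be completed on received data only". Section 9.10 confines sensitivity analyses to the primary outcome.

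**Appendix D7.** All-cause mortality within 3 hours appears twice, each time with n/N, relative risk, absolute risk difference and a p-value. Footnote 9, attached to the second appearance, restricts it to participants with an exact time of death. It defines no denominator.

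**Lactate component (section 9.4).** Death before the interval sample counts as failure to clear. The timing requirement reads: "For this we require the date and time of death from the exit form to determine if the participant died within two hours"; with the half hour that the sentence then adds, the limit is 2.5 hours. This passage makes no assumption about on-scene deaths, whereas the 3-hour and 30-day mortality definitions both do.

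**The concern.** Three rules, followed as written, give a worse result than the data allow.

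1. A participant who withdraws alive on, say, day 5 has no time of death and no exit by discharge. No branch applies, and a received-data analysis drops them. Yet vital signs are collected to 24 hours after arrival at the emergency department (section 4.4) and assessments run daily to day 30 (section 4.5), so survival past 3 hours will usually be on record.
2. Survivors have no time of death. A row restricted to people who have one is conditioned on the outcome and is not a comparison of the randomised groups.
3. The same untimed on-scene death is a certain event in two mortality outcomes but can be left uncoded in the lactate component, although it must have preceded the 2-hour sample.

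At stake are the two 3-hour mortality results, the lactate component row in Appendix D7, the split of qualifying events in Appendix D6a and the Bayesian lactate analysis in Appendix D10b.

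**Working it through.** The SAP states no 3-hour mortality, total mortality or withdrawal rate, so there is no figure to reproduce. All rates below are assumptions except the 10% loss allowance (section 4.7), which is an overall planning figure and not a withdrawal rate.

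**1. Withdrawn survivors dropped.** With true 3-hour risk p and share w withdrawn alive and uncoded, the reported risk is p/(1-w).

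| w | p = 20% is reported as |
|---|---|
| 1% | 20.2% |
| 2% | 20.4% |
| 5% | 21.1% |
| 10% | 22.2% |

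At w = 10% the factor is 1/0.90 = 1.11. The reported relative risk is the true one times (1-w_C)/(1-w_P), with C for crystalloid and P for PHBP.

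- Equal w in both arms: relative risk unchanged. With 20% vs 15% and w = 10%, the risk difference goes from -5.0 to 16.7 - 22.2 = about -5.6 points.
- w_C = 2%, w_P = 5%, no true effect: 0.98/0.95 = 1.03.
- w_C = 0%, w_P = 10%, no true effect: 1/0.90 = 1.11.

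The rule also leaves some deaths uncoded. Only untimed deaths on scene are assumed events. The notes to Appendix D2a expect deaths in transit as well, and an untimed death there meets no branch. Losses can therefore occur on both sides, and the net direction is not fixed.

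**2. The footnote 9 row.** Take 3-hour deaths of 15% (PHBP) vs 20% (crystalloid), a true relative risk of 0.75.

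Literal reading, where the denominator is deaths with a recorded time:

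- 20% later deaths in each arm: (15/35)/(20/40) = 0.429/0.500 = 0.86.
- Total deaths 40% vs 45%: (15/40)/(20/45) = 0.375/0.444 = 0.84.
- Total deaths 30% vs 45%: (15/30)/(20/45) = 0.500/0.444 = 1.13, so the direction reverses.

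Likely intended reading, where survivors stay in and only untimed deaths go out:

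- No untimed deaths: 0.75, no change.
- 2 of 15 vs 5 of 20 early deaths per 100 untimed: (13/98)/(15/95) = 0.133/0.158 = 0.84.
- 5 untimed early deaths per 100 in each arm: (10/95)/(15/95) = 0.67.

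On this reading too, the row removes people because of their outcome, and the result can shift either way.

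**3. Untimed on-scene death across the outcomes in section 9.4.**

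| Outcome | Coding as written |
|---|---|
| Episode mortality | Event (on-scene deaths are included) |
| Primary composite | Event, through episode mortality |
| 3-hour mortality | Assumed event |
| 30-day mortality | Assumed event |
| Lactate component | Time of death asked for; no on-scene assumption |

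If a share u of an arm falls in the last row uncoded, a failure risk f is reported as (f-u)/(1-u), which is too low. In Appendix D6a the SAP does not settle whether such a participant belongs with both events, with mortality alone, or with missing.

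**The case against.** The strongest reply is that these are wording gaps in secondary outcomes. Much of it stands.

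- Participants still in hospital at day 30 are not lost, because episode mortality is followed to discharge. Withdrawal is the only exit route without a branch.
- The 10% allowance covers all loss to follow-up. It says nothing about how many withdraw alive or whether the arms differ.
- Participants who withdrew consent for use of their data are handled separately in section 5.5 and are rightly left uncoded.
- Two 3-hour rows placed together suggest that the second was meant only to show the result without the on-scene assumption. The 0.86 and the reversal to 1.13 need the literal reading.
- The lactate criterion is death before interval sampling. The request for a time need not mean that untimed on-scene deaths become missing.

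A reader might infer that both 3-hour results are distorted, that known survivors are lost but deaths never are, or that 3-hour mortality is necessarily inflated. The SAP does not support this: untimed deaths off scene are also uncoded, no withdrawal figures are given, and the relative risk in the main row is unchanged when withdrawal is equal.

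What remains is that the rules, applied literally, drop known survivors, permit a table row without survivors, and leave certain lactate failures uncoded. No planned sensitivity analysis would reveal the effect on 3-hour mortality.

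**Conclusion.** The point holds for secondary outcomes. The primary composite does not change, because an on-scene death is already an event through episode mortality.

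For the main 3-hour row, the effect of dropped survivors is bounded: a factor of 1.11 on the risk if 10% of an arm were withdrawn alive, and less at lower rates. Bias in the relative risk needs withdrawal to differ by arm, on which the SAP is silent.

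The footnote 9 row is the weaker result. Read literally, it reports the share of timed deaths that were early. On the kinder reading, it still excludes certain early deaths by outcome. The sizes shown rest on assumed death rates.

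The lactate inconsistency affects the component row in D7, Appendix D6a and Appendix D10b. Its size depends on how many on-scene deaths lack a time, which the SAP does not give.

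The 30-day rule shares the withdrawal gap, but there survival status after withdrawal may be truly unknown.

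**What to change.** 1. **3-hour rule.** Code as a non-event every participant with a usable record of being alive more than 3 hours after randomisation: later vital signs, a daily assessment, or an exit or death on a later day. Where only a date is held, check that it rules out the first 3 hours, since a randomisation after 21:00 leaves less than 3 hours before midnight. Exempt participants who withdrew consent for use of their data (section 5.5). State how untimed deaths off scene are coded when the date does not settle the matter.
2. **Footnote 9.** Delete the row, or define it as a sensitivity analysis in which survivors stay as non-events, on-scene deaths stay as events, and only untimed deaths off scene are varied between event and non-event. State the denominator.
3. **Lactate component.** State that a death on scene without a recorded time counts as death before interval sampling, so that the D7 component row, D6a and D10b agree with the mortality outcomes.

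The cost is SAP wording and programming, using records that the SAP already plans to collect. The SAP does not say whether a withdrawal date is captured, so the rule should not depend on that item alone. Design, sample size and primary analysis stay as they are.
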